11.0 ENDPOINT EVALUATION CRITERIA/MEASUREMENT OF EFFECT

11.1 Response/Progression

Disease response/progression will be evaluated using 2014 Lugano Classification (see [Appendix B](#))^{8,11}. Participants who meet the definition of progressive disease per Lugano Classification should be evaluated using the LYRIC criteria¹⁰ (see [Appendix C](#)). The ORR and CR rate will also be estimated according to the International Harmonization Project response criteria (Cheson 2007).⁹

PET-CT or diagnostic quality CT of the neck, chest, abdomen, and pelvis (N/C/A/P) with IV contrast will be performed at baseline (within the screening window, 28 days) prior to initiation of study therapy, and then after initiation of study therapy during cycle 4 and every 4 cycles thereafter until disease progression or off study therapy. Refer to [study calendar \(footnote r\)](#) for disease staging at EOT. Disease staging will be by either PET/CT (preferred) or CT scan, but, in patients with FDG-avid disease, it will be preferred (but not mandatory) to have PET/CT at baseline, Cycle 4 and at least every 8 cycles thereafter. In patients with FDG-avid disease, CR must be confirmed with PET/CT. Patients who enter CR with study therapy can be monitored with diagnostic quality CT scans thereafter until disease progression. MRI may be performed at the investigator's discretion for lesions not well-visualized by CT, or if CT with intravenous contrast is contraindicated. PET-CT and CT results will be read by radiology at each study site and investigator response based on radiology reading will be performed. Lymphoma response assessment based on PET-CT/CT will be based on the 2014 Lugano Classification ([Appendix B](#)).^{8,11}

Note: if there is no evidence of neck involvement by lymphoma at baseline, CT of chest, abdomen and pelvis (C/A/P) can be performed instead of N/C/A/P at subsequent re-staging.

Following initial screening, and unless clinically indicated, bone marrow specimens will be collected only to confirm CR.

For patients with progression of disease on imaging, it is strongly recommended that a confirmatory biopsy (performed as standard of care) be obtained whenever possible. Note that only an FDG-negative PET scan will be considered complete remission in patients whose tumor was FDG-avid at baseline.

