5.2 Treatment Cycle Definition

In the absence of a delay due to toxicity, each treatment cycle lasts 21 days \pm 3 days. Day 1 of a cycle is defined as the administration of pembrolizumab.

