5.10 Duration of Therapy and Criteria for Removal from Protocol Therapy

Participants will receive protocol therapy until one of the below criteria are met:

- Disease progression
- **Note:** Following consultation with the Study PI, participants who meet progression per 2014 Lugano classification⁸ but who meet the criteria of “indeterminate response” (IR) according to the provisional modification to the 2014 Lugano Classification, the LYRIC criteria¹⁰ ([Appendix C](#)), and are deriving clinical benefit may continue to receive protocol therapy beyond progression as long as they meet the following criteria:
 - Continue to meet treatment criteria
 - Investigator-assessed clinical benefit
 - Tolerance of study drug
 - Stable performance status
 - Treatment beyond progression will not delay an imminent intervention to prevent serious complications of disease progression (e.g., CNS metastases)
- *If the patient has IR per LYRIC criteria and is receiving therapy beyond progression:*
 - A confirmatory PET-CT should be performed within 12 weeks after initial progression to determine whether the patient meets PD criteria according to the LYRIC criteria¹⁰.
 - Further progression is defined according to the LYRIC criteria
 - Protocol therapy should be discontinued permanently upon documentation of PD per the LYRIC criteria
- Unacceptable toxicity despite dose delay/ modification

- **Note:** If one agent is delayed due to toxicity, then participants may continue with monotherapy for the other agent.
- Completed protocol therapy.
- General or specific changes in the participant's condition (including intercurrent illness) which render the participant unacceptable for further treatment in the judgment of the investigator
- Withdrawal of consent for further protocol therapy by the participant (See Section 16.5)

Once participants meet criteria for removal from protocol therapy, the participant should then proceed to End of Protocol Therapy assessments and follow-up.

Documentation of the reason for discontinuing protocol therapy and the date effective should be made in the medical record and appropriate eCRF. The COH DCC and the Study PI should be promptly notified of the change in participant status.

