6.3 Dose Delay/ Modification Guidelines for Pembrolizumab-associated Adverse Events

- Toxicities will be graded using the [NCI CTCAE Version 5.0](#).
- Baseline values are from the last values obtained prior to treatment.

AEs associated with pembrolizumab exposure may represent an immunologic etiology. These immune-related AEs (irAEs) may occur shortly after the first dose or several months after the last dose of pembrolizumab treatment and may affect more than one body system simultaneously. Therefore, early recognition and initiation of treatment is critical to reduce complications. Based on existing clinical study data, most irAEs were reversible and could be managed with interruptions of pembrolizumab, administration of corticosteroids and/or other supportive care. For suspected irAEs, ensure adequate evaluation to confirm etiology or exclude other causes. Additional procedures or tests such as bronchoscopy, endoscopy, skin biopsy may be included as part of the evaluation. Based on the severity of irAEs, withhold or permanently discontinue pembrolizumab and administer corticosteroids. Dose modification and toxicity management guidelines for irAEs associated with pembrolizumab are provided in Table 6.3.

Table 6.3 Dose Modification and toxicity management for irAEs typically associated with pembrolizumab

General instructions:

1. Corticosteroid taper should be initiated upon AE improving to Grade 1 or less and continue to taper over at least 4 weeks.
2. For situations represented in Table 6.3 where pembrolizumab has been withheld, pembrolizumab can be resumed after AE has been reduced to Grade 1 or 0 and corticosteroid has been tapered. Pembrolizumab should be permanently discontinued if AE does not resolve within 12 weeks of last dose or corticosteroids cannot be reduced to ≤ 10 mg prednisone or equivalent per day within 12 weeks.
3. For situations represented in Table 6.3 where pralatrexate has been withheld, pralatrexate can be resumed at prior dose after AE improves to grade 1 or 0. If the investigator feels that the AE was related to pralatrexate, the pralatrexate dose can be reduced by one level after discussion with the overall study PI.

Exceptions:

- For patients who develop severe renal impairment (eGFR or CrCl 15 to < 30 mL/min/1.73m 2) while on treatment with pralatrexate at the 30 mg/m 2 dose level, the dose of pralatrexate upon recovery will be reduced to 15 mg/m 2 .

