- Safety visit to occur 30 (-2/+7) days post-last dose of protocol therapy. At the end of the treatment, each subject will be followed for 30 days for adverse event monitoring, and 90 days for severe adverse events and events of clinical interest. Safety follow up may be extended until resolution/stabilization of reportable AEs.
- Protocol therapy will continue for a maximum of 24 months until progressive disease, unacceptable toxicity, withdrawal of consent, pregnancy of the subject, non-compliance, or administrative reasons.
- Leucovorin will be administered orally three times daily (every 8 hours) for 2 days for a total of 6 doses **beginning 24h (+/- 2h) after each dose of pralatrexate** is administered. Refer to [Section 5.13.2](#).
- Vitamin B12 (1 mg IM) will be administered anytime within 10 weeks prior to initiation of pralatrexate (per pralatrexate product insert) and can be administered during screening, and will be administered every 3 cycles. Administration should continue during the full course of pralatrexate therapy and for 30 days after the last dose of pralatrexate. Refer to [Section 5.13.2](#).
- Vital signs: Weight, heart rate, blood pressure, respiration rate, and temperature. Height required only at baseline.
- To be done between D15 and D21 (-3 days).

- h. Disease staging is performed at screening and every 4 cycles until disease progression or off study therapy. Disease staging will be by either PET/CT (preferred) or CT scan, but, in patients with FDG-avid disease, it will be preferred (but not mandatory) to have PET/CT at baseline, Cycle 4 and every 8 cycles thereafter. Note: if there is no evidence of neck involvement by lymphoma at baseline, CT of chest, abdomen and pelvis (C/A/P) can be performed instead of N/C/A/P at subsequent re-staging.
- i. Tumor biopsy tissue will be obtained after routine diagnostic biopsy is done with the patient's consent. Exception can be granted by the PI if a biopsy is not feasible and/or safe. For the EOT time point, tumor tissue will be collected from a standard of care tumor biopsy performed at the time of lymphoma relapse/progression (if such a biopsy is performed), unless the tumor is inaccessible or there is a safety concern.
- j. Following initial screening, and unless clinically indicated, bone marrow specimens will be collected only to confirm CR.

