12.0 STATISTICAL CONSIDERATIONS

12.1 Study design overview

This is a multi-center, single arm phase 1/2 study of pembrolizumab plus pralatrexate for patients with relapsed/refractory PTCL. Patients will receive 21-day cycles of the combination therapy up to 2 years until disease progression, unacceptable toxicity, or until the patient meets any criteria for removal from protocol therapy in [Section 5.10](#), whichever is earlier. Response will be assessed every 4 cycles. The phase 1 dose-escalation portion of the study, with 2 dose levels and 1 possible de-escalation dose level ([Table 5.3](#)), will determine the MTD and the RP2D of the combination therapy. After the completion of the phase 1 portion, additional patients will be enrolled and treated at the RP2D in the Phase 2 portion. Another primary endpoint is overall response rate per the Lugano classification.⁸ Secondary endpoints include CR rate, duration of response, overall survival, progression-free survival, ORR and CR rate per the International Harmonization Project response criteria (Cheson 2007)⁹ and response status based on LYRIC criteria¹⁰.

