APPENDIX C: LYRIC CRITERIA

Lugano Classification was developed based on treatment with cytotoxic agents⁸. Immunotherapeutic drugs, may produce antitumor effects by potentiating endogenous cancer-specific immune responses. The response patterns seen with such an approach may extend beyond the typical time course of responses seen with cytotoxic agents, and can manifest as clinical responses after initial increases in tumor burden or even the appearance of new lesions. Thus, the 2014 Lugano Classification may not provide an accurate assessment of response to immunotherapeutic agents. Provisional modification of the Lugano criteria (LYRIC Criteria) may be used to assess participants who meet progressive disease per Lugano Classification^{8,10}.

Complete Response	Partial Response	Progressive Disease
Same as Lugano	Same as Lugano	
As with Lugano with the following exceptions:
 
Indeterminate response (IR)
 
 IR1: ≥50% increase in SPD of up to 6 measurable lesions in first 12 weeks of therapy without clinical deterioration IR2: <50% increase in the overall SPD with 
 a. Appearance of a new lesion(s), or b. ≥50% increase in PPD of a lesion or set of lesions at any time during treatment IR(3): Increase in FDG uptake without a concomitant increase in lesion size or number 
Patients with IR should continue on therapy and have repeat imaging after an additional 12 weeks (or sooner if clinically indicated).
 
Progressive disease criteria in these patients will be met if:
 
 IR1: An additional increase in the target SPD of ≥ 10% between the first IR1 timepoint and the SPD being assessed; or an increase in ≥ 5mm in either dimension of at least one lesion for lesions ≤ 2cm and 10mm for lesions > 2cm. IR2: the new or growing lesion(s) should be added to the target lesions (total of no more than 6) and there is PD if the SPD if the newly defined set of target lesions has increased ≥50% from their nadir value (which may precede the IR time point). IR3: There is evidence of PD by an increase in lesion size or the development of new lesions.

Abbreviations: SPD, sum of the product of the diameters; PPD, product of the perpendicular diameters.

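### Scheduled scans follow cycle number and a cycle starts only with pembrolizumab, so a pembrolizumab hold postpones scans and a permanent stop leaves their dates undefined

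*Combined protocol and SAP*

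**What the plan says.** All references are to the combined protocol and SAP.

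- **Scan schedule.** Section 11.1 places imaging "during cycle 4 and every 4 cycles thereafter until disease progression or off study therapy". Section 12.1 agrees: "Response will be assessed every 4 cycles". Table 10, footnotes g and h, puts the scan at Days 15 to 21 of the cycle, with a 3-day early allowance.
- **Cycle definition.** Section 5.2: "Day 1 of a cycle is defined as the administration of pembrolizumab". The nominal length is conditional: "In the absence of a delay due to toxicity, each treatment cycle lasts 21 days", with ±3 days.
- **Holds.** Section 5.10: "If one agent is delayed due to toxicity, then participants may continue with monotherapy for the other agent". Section 6.2 likewise lets pralatrexate go on when the toxicity is attributed to pembrolizumab. The limit on a hold is in Section 6.3: "Pembrolizumab should be permanently discontinued if AE does not resolve within 12 weeks of last dose".
- **Permanent stop.** Several rows of Table 6.3 end pembrolizumab but only hold pralatrexate. General instruction 3 and the neurological row foresee that pralatrexate may resume.
- **Counting rule for one agent.** Table 10, footnote m, covers only the patient who stops pralatrexate and stays on pembrolizumab.
- **LYRIC.** Appendix C allows IR1 only for a rise of at least 50% in SPD "in first 12 weeks of therapy without clinical deterioration".
- **Off treatment.** Table 10, footnotes q and r, sets scans by calendar, every 12 weeks from the last scan in the first year.

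**The concern.** Dose timing sets the scan clock. When pembrolizumab is held, no new cycle begins and no scan falls due, although the patient may still be receiving pralatrexate. Section 11.2 dates PFS at the first observation of progression, so a later scheduled scan means a later PFS event. Patients with toxicity would be imaged less often than patients without, and less often than patients who have left treatment. There is no control arm to share the lag when PFS is read against historical figures.

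The permanent-stop case is a plain gap. A patient on pralatrexate alone is still on study therapy, so the off-treatment calendar does not apply, and Section 5.2 supplies no further Day 1 from which to count four cycles.

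The IR1 limit runs in calendar time while the first scan runs in cycle time. A delay before cycle 4 can therefore decide whether a large early increase is labelled IR1 or PD. Under Section 5.10 that label bears on whether continuing therapy may be considered.

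**Working it through.** **1. The plan's own conversion.** Section 5.5 gives the two-cycle DLT period as 42 days without delay: 2 × 21 = 42, reproduced. Four cycles are 4 × 21 = 84 days = 12 weeks, the interval used in response follow-up.

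**2. Longest single hold.** The 12 weeks in Section 6.3 run from the last dose and already contain the normal 21-day gap. If the next dose is given by that limit, Day 1 is at most 84 − 21 = 63 days late. The scan interval becomes (84 + 63)/7 = 21 weeks instead of 12. Section 2.1.1 quotes a single-agent median PFS of 3.5 months: 3.5 × 30.4375/7 ≈ 15.2 weeks.

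**3. First scan against the IR1 limit.** Elapsed days from C1D1 (C1D1 = 0) are 3 × 21 + delay + (day of cycle − 1). Study day is one higher.

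| Delay of C4D1 (days) | D12 (3 days early) | D15 | D21 |
|---|---|---|---|
| 0 | 74 | 77 | 83 |
| 7 | 81 | 84 | 90 |
| 10 | 84 | 87 | 93 |
| 11 | 85 | 88 | 94 |
| 21 | 95 | 98 | 104 |
| 63 | 137 | 140 | 146 |

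If 12 weeks means elapsed day 84, the slack is 84 − 77 = 7 days from D15 and 84 − 74 = 10 from D12. If it means study day 84 (elapsed 83), the slack is 6 and 9. Beyond that, no permitted scan date falls inside the window.

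Two routine ways to use up the slack:
- Three cycles at the permitted 24 days put C4D1 at 72, so D15 is at 72 + 14 = 86 and D12 at 83, with no toxicity at all.
- Table 6.3 asks for a steroid taper of at least 4 weeks. If the taper must be finished before redosing and the event improves y days after the last dose, the next dose is y + 28 − 21 = y + 7 days late. From y = 4, that is 11 days or more.

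**4. Illustration of the lag (assumptions mine).** Assume exponential time to progression with median 15.2 weeks, detection at scheduled scans only, first scan at s weeks and then every 12. With λ = ln 2/15.21875, the mean lag is s + 12·exp(−λs)/(1 − exp(−12λ)) − 1/λ.

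| Hold before first scan | s (weeks) | Mean lag (weeks) |
|---|---|---|
| none | 11.5 | 6.42 |
| 3 weeks | 14.5 | 7.27 |
| 6 weeks | 17.5 | 8.39 |
| 9 weeks | 20.5 | 9.75 |

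These are for a patient who has the hold. If 10% of patients have a 3-week hold, the average over all patients is 6.42 + 0.1 × 0.85 ≈ 6.5 weeks. If 50% have a 9-week hold, it is 6.42 + 0.5 × 3.33 ≈ 8.1.

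**The case against.** The case for leaving the plan alone has weight.

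- **Unscheduled imaging is allowed.** Section 5.9 and Table 10 permit extra procedures when clinically indicated, Section 5.7 encourages imaging to confirm early clinical progression, and PFS counts any first observation. This stands: the lags above are upper illustrations. Symptom-driven imaging is still not a fixed schedule.
- **Long single-agent periods are a subset.** Table 6.3 also holds pralatrexate for many events, and Section 6.4 ends it after more than 28 days without a dose. This stands too. But while both agents are held no cycle begins either, and the calendar schedule starts only once the patient is off protocol therapy.
- **The endpoints are secondary.** PFS and duration of response are untested Kaplan–Meier estimates in one arm. ORR counts response at any time during treatment and is little affected.

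A reader might also infer more than the text supports:

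- *The interval can double to 24 weeks.* That counts the normal three-week gap twice.
- *A one-week delay always closes IR1.* The early allowance keeps a permitted scan date inside the window.
- *Any hold turns IR into PD.* Only delay before C4D1 matters, and only for IR1. IR2 and IR3 carry no 12-week limit.
- *Duration of response is inflated.* A hold after response is documented delays PD and lengthens it. A hold before the first scan delays the documented start and can shorten it.

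**Conclusion.** The point holds as a scheduling gap, and it is a cheap improvement rather than a threat to the primary result. Sections 5.2, 5.10, 6.2 and 11.1 together let a pembrolizumab hold postpone scheduled scans, and they define no on-treatment scan date after a permanent pembrolizumab stop with pralatrexate continuing.

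One maximal hold stretches an interval from 12 to about 21 weeks. This assumes a single hold and redosing by the 12-week limit. PFS then tends to run long in patients with holds. By how much overall cannot be said, because the documents give no hold rate and the lag figures rest on an assumed exponential model.

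For LYRIC, a delay of C4D1 beyond about 6–7 days (9–10 with the early allowance) puts the first scheduled scan outside the IR1 window. An overall SPD rise of at least 50% first seen there is PD and not IR1.

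**What to change.** In Section 11.1, Table 10 (with footnotes g and h) and Section 12.1, anchor disease assessment to C1D1 by calendar:

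- First scan in weeks 11–12, with the window closing by day 84 and no plus allowance. A ±7-day allowance here would admit week 13 and defeat the purpose.
- Then every 12 weeks (±7 days), regardless of dose holds or continuation on one agent, as in response follow-up.
- Restate the PET/CT preference, now every 8 cycles, as every 24 weeks (8 × 21 = 168 days), so that the two schedules stay aligned.

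**Cost.** This is an amendment of wording. Patients without delays have the same number of scans. Scans may no longer coincide with a cycle visit, and patients with delays may have somewhat more scans per cycle. No dosing or treatment-continuation rule changes.

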11.2 Clinical Endpoint Definitions

Overall Response Rate (ORR): Defined as the proportion of patients that have a documented CR or PR at any time during study treatment.

Complete Response (CR) rate: Defined as the proportion of patients that have a documented CR at any time during study treatment.

Duration of Response (DOR): Defined as the time from the first achievement of PR or CR to time of PD. Patients who never achieve PR or CR are excluded. Patient who has not had disease progression/relapse at last follow-up is censored at the time of last follow-up.

Overall Survival (OS): Defined as time from initiation of study therapy to death from any cause. If a patient is alive at the last evaluation time period, survival time is censored at the time of last follow-up.

Progression-Free Survival (PFS): Defined as the time from initiation of study therapy to the first observation of disease relapse/progression or death from any cause, whichever occurs first. If the patient has not progressed relapsed or died, the patient is censored at the time of last follow-up.

Toxicity: Toxicity and adverse events will be recorded using the NCI CTCAE 5.0 scale. Observed toxicities will be summarized by type (organ affected or laboratory determination such as absolute neutrophil

count), severity (by NCI CTCAE v5.0 and nadir or maximum values for lab measures), date of onset, duration, reversibility, and attribution.

Unacceptable Toxicity: defined as one of the following AEs that is at least possibly related to study treatment:

- Any **≥ grade 3 immune-related AE (IrAE)** that does not resolve to grade ≤ 1 within 7 days with the exception of:
 - Grade 3 immune-related hepatitis if ALT or AST < 8 x ULN or total bilirubin < 5 x ULN.
 - Grade 3 asymptomatic endocrinopathy.
 - Inflammatory response attributed to local antitumor response.
 - Vitiligo or alopecia of any grade.
- Any non-hematologic **grade 4 AE** that does not resolve to grade ≤ 1 within 7 days with the exception of:
 - Grade 4 asymptomatic lipase or amylase without evidence of pancreatitis
 - Grade 4 asymptomatic laboratory abnormalities including, but not limited to, hypo- or hyperglycemia, hypo- or hypernatremia, hypo- or hyperkalemia, hypo- or hypermagnesemia, hypo- or hyperphosphatemia, or hyperuricemia that do improve within 48 hours to Grade ≤ 2 with supportive measures.
 - Inflammatory response attributed to local antitumor response.
- Any Grade 5 AE.

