5.11 Follow-Up

Following completion of protocol therapy, all participants will enter follow-up after ending protocol treatment. This is comprised of:

- **Safety Follow-up-** 30 days post-last dose of protocol therapy through to (a) 90 days post-last dose of protocol therapy or (b) until initiation of a new anticancer therapy (whichever occurs sooner)
- Note: the period for safety follow-up will be extended until stabilization or resolution for all reportable AEs (per the agreement of the Study PI) and accompanying follow-up safety report.
- **Response Follow-up-** for those who have yet to have disease progression.
- **Survival Follow-up-** for those who progressed or completed Response Follow-up.

This follow-up will be performed typically via medical record review. It will entail (a) Disease status (for those who have yet to progress) (b) Vital status (all participants).

Assessment time points and windows are detailed in [Section 10.0](#).

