6.1.2 Pralatrexate

Per package insert: the most common adverse reactions (>35%) are mucositis, thrombocytopenia, nausea, and fatigue. Most common serious adverse reactions are pyrexia, mucositis, sepsis, febrile neutropenia, dehydration, dyspnea, and thrombocytopenia.

Bone Marrow Suppression

Pralatrexate can suppress bone marrow function, manifested by thrombocytopenia, neutropenia, and anemia.

Mucositis

Treatment with pralatrexate may cause mucositis.

Dermatologic Reactions

Pralatrexate has been associated with severe dermatologic reactions, which may result in death. Dermatologic reactions have been reported in clinical studies and post-marketing safety reports in patients treated with pralatrexate. Dermatologic reactions have included skin exfoliation, ulceration, and toxic epidermal necrolysis (TEN) (post-marketing reports). These reactions may be progressive and increase in severity with further treatment, and may involve skin and subcutaneous sites of known lymphoma.

Tumor Lysis Syndrome

Tumor lysis syndrome has been reported in patients with lymphoma receiving pralatrexate in post-marketing reports.

Hepatic Toxicity

Hepatic toxicity and liver function test abnormalities have been observed after pralatrexate administration. Persistent liver function test abnormalities may be indicators of liver toxicity.

Risk of Increased Toxicity in the Presence of Impaired Renal Function

Patients with moderate to severe renal function impairment may be at greater risk for increased exposure and toxicity. Serious adverse drug reactions including TEN (post-marketing reports) and mucositis were reported in patients with end stage renal disease (ESRD) undergoing dialysis who were administered FOLOTYN therapy.

Pregnancy and Breastfeeding

Pralatrexate can cause fetal harm when administered to a pregnant woman. Pralatrexate was embryotoxic and fetotoxic in rats and rabbits.

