7.7 Expedited Reporting

Table 7.7 indicates what events must be reported expeditiously.

Table 7.7 Criteria for Expedited Reporting

Time point	What to report expeditiously
From the signing of the consent to study completion	All unanticipated problems
From Screening until Day 1 of protocol therapy	
 • All SAEs related to protocol procedures • Pregnancy and lactation • Any reason for not starting Day 1 of protocol therapy
For the time period beginning at treatment through 90 days following cessation of treatment, or 30 days following cessation of treatment if the subject initiates new anticancer therapy, whichever is earlier	
 • All SAEs regardless of relationship to protocol therapy, study procedure, underlying disease or concomitant treatment. • Death due to any cause other than progression of the cancer under study. • All AEs that meet the definition of an unanticipated problem. • Overdose of either agent. • Pregnancies and lactation. • Abnormal liver function tests • Discontinuation of protocol therapy due to unusual or unusually severe AE considered related to protocol therapy
For participants yet to initiate anti-cancer therapy: From Day 1 of therapy up to 120 days post-last pembrolizumab dose	
 • Pregnancies and lactation.
Post Safety follow-up to removal from study	
 • All SAEs that are considered possibly, probably, or definitely related to pembrolizumab

NOTE: All events reported expeditiously require follow-up reporting until the event is resolved, stabilized, or

determined to be irreversible by the investigator.

The DCC should be consulted prior to ending the follow-up of events that have stabilized.

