12.3.3 Analysis of Anti-tumor Activity

This study will aim to obtain an estimate of the anti-tumor activity of the study combination. ORR will be calculated as the proportion of evaluable patients that have confirmed CR or PR, as defined according to the 2014 Lugano Classification, exact 95% confidence intervals will be calculated for these estimates. Response rates will also be evaluated based on number and type of prior therapy(ies). Duration of response, as well as progression-free survival and overall survival will be estimated using the product-limit method of Kaplan and Meier. As secondary endpoints, the ORR and CR rate will also be estimated according to the International Harmonization Project response criteria (Cheson 2007).⁹

Any patient treated at the RP2D, including those from the Phase 1 portion, will be included in efficacy analyses. Patients will be evaluable for efficacy assessment if they received at least one dose of pralatrexate and at least one dose of pembrolizumab and underwent at least one response assessment. As discussed in [Section 5.7](#), patients will be evaluable for efficacy if they discontinued study therapy prior to the first response assessment because of progression of disease rather than solely because of unacceptable toxicity, withdrawal of consent, or investigator's decision.

12.3.4 Safety Analysis and Stopping Rules for Excessive Toxicity or for Rapid Disease Progression

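### Duration of response ends only at PD, so a responder who dies without PD is censored in the Kaplan-Meier estimate although the same death is a PFS event

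*Combined protocol and SAP*

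**What the plan says.** Section 11.2 defines DOR as "Defined as the time from the first achievement of PR or CR to time of PD". Its censoring sentence reads "Patient who has not had disease progression/relapse at last follow-up is censored at the time of last follow-up". Neither sentence mentions death.

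In the same section the PFS event is the "first observation of disease relapse/progression or death from any cause, whichever occurs first". The PFS censoring sentence leaves out patients who died: "If the patient has not progressed relapsed or died, the patient is censored at the time of last follow-up".

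Section 12.3.3 states the estimator for all three time-to-event endpoints together: "Duration of response, as well as progression-free survival and overall survival will be estimated using the product-limit method of Kaplan and Meier". It names no competing-risk method and no separate event rule for DOR. The synopsis and Section 1.2 list DOR as secondary without defining it again.

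**The concern.** Kaplan-Meier treats a censored patient as having the same prospects as those still at risk. That suits a responder who is alive when follow-up ends. A responder who has died cannot remain in response, so censoring the death gives an estimate of freedom from progression as if death did not occur. Most readers take a Kaplan-Meier DOR to mean time alive in response.

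The plan allows for deaths that are not progression. Table 7.7 lists for expedited reporting "Death due to any cause other than progression of the cancer under study", and Section 6.1.2 warns that "Pralatrexate has been associated with severe dermatologic reactions, which may result in death". Section 12.3.4 monitors treatment-related mortality.

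At stake is the reading of one secondary endpoint, estimated in few patients, where a single death can change the reported median.

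**Working it through.** The plan states no DOR median, event count or precision, so there is no figure to reproduce. The check applies its rule as written and compares the result with death counted as an event.

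**Inputs**
- 24 response-evaluable patients and a single-agent ORR of 29% (Section 12.1.2).
- Responders: 0.29 × 24 = 6.96, about 7. If ORR were 50% (assumed): 0.50 × 24 = 12.
- f = share of response-ending events that are deaths without PD. The documents do not give it. Assumed range 0% to 30%.

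**1. Constant hazards, censoring on the death date.** The PD-only median is ln2/h_PD. The median for PD or death is ln2/(h_PD + h_death). Their ratio is 1/(1 − f). When 50% are truly alive in response, the PD-only curve reads 0.5^(1 − f).

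| f | Median ratio | PD-only curve when the true value is 50% |
|---|---|---|
| 0% | 1.00 | 50% |
| 5% | 1.05 | 52% |
| 10% | 1.11 | 54% |
| 20% | 1.25 | 57% |
| 30% | 1.43 | 62% |

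**2. One death, k responders at risk.** Counting the death multiplies the curve by (k − 1)/k; censoring it does not. The PD-only curve is therefore k/(k − 1) times as high just afterwards: 7/6 = 1.17 with 7 at risk, 4/3 = 1.33 with 4 at risk. It stays above the other curve until the one that counts the death reaches zero.

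**3. Effect on the median, censoring on the death date.** Take 7 responders, all with an event, and the median as the first time the curve is at or below 0.5. With every event counted, the median is the 4th ordered time.
- One death at rank 2, 3 or 4, if censored, moves the median to the 5th time. At rank 1, 5, 6 or 7 it stays. So it moves in 3 of 7 orderings (43%).
- Two deaths: it moves in 15 of 21 (71%).
- With 12 responders: 6 of 12 (50%) for one death, 51 of 66 (77%) for two.
- In this setting the median never shortens.

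Weighting the 7-responder results by Binomial(7, f):

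| f | At least one death in response | Median moves |
|---|---|---|
| 5% | 30% | 14% |
| 10% | 52% | 27% |
| 20% | 79% | 49% |
| 30% | 92% | 66% |

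**4. Censoring at an earlier last follow-up.** Section 11.2 does not tie last follow-up to the death date or to a disease assessment. Take 7 responders, six with PD and one who dies after the third PD but whose last follow-up precedes the first PD. Censoring leaves 6 at risk, and the curve runs 5/6, 4/6, 3/6, so the median is the third PD. With the death counted, the curve after the third PD is 4/7 = 0.57, so the median comes later. Here the plan's rule shortens the median. With one death, the same happens for 9 and 11 responders and not for 6, 8, 10 or 12.

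**5. Sampling error for scale.** With 7 events, the exponential 95% interval runs from 14/26.12 = 0.54 to 14/5.63 = 2.49 times the estimate. That is wider than any shift in the first table.

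**The case against.** **PD-only may be deliberate.** Time to progression among responders is a possible endpoint, and it would sit beside PFS and OS, which count every death. This stands in part. DOR and PFS are different endpoints, so a reader who infers that the two definitions contradict each other goes too far. What remains is that the plan does not say the omission is intended, and Kaplan-Meier with deaths censored is then easily misread.

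**Some deaths may be entered as PD.** The DOR definition does not require documented PD. Sections 5.7 and 12.3.3 accept progression before the first response assessment, and 5.7 only encourages imaging. A lymphoma death might therefore be recorded as PD. This stands, so the clear gap is a non-lymphoma death in response.

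**The bias need not be favourable.** A reader might infer that the rule can only lengthen DOR. Step 4 of the working shows that this holds only when the patient is censored on the death date, which the plan does not specify.

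**The size is unanchored.** A reader might also infer from Table 7.7 and Section 6.1.2 that deaths in response are expected. One is a reporting list and the other a general drug warning; neither gives a rate among responders. The percentages are illustrations.

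**Counting deaths has its own problem.** Study calendar footnote q assures response follow-up for at least one year in patients who have not progressed. Footnote z then continues survival follow-up by records, registry or telephone. If late deaths are events while comparable survivors are censored at their last scan, DOR can be biased downward. This stands, and the fix has to deal with it.

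**Conclusion.** The point holds for the definition as written: a responder who dies without PD is a PFS event and a DOR censoring, and nothing elsewhere in the plan changes that. With censoring on the death date, the curve is higher from then on and the median is unchanged or longer. With censoring at an earlier last follow-up, the median can occasionally be shorter.

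The effect is zero if no such death occurs. The increases of 5% to 43% in the median rest on constant hazards and on assumed shares of 5% to 30%. The chances that the median moves also assume that all responders have an event. A wide interval does not remove a known bias, but it keeps the point in proportion. Deaths remain visible in PFS and OS, although PFS covers all patients and so does not correct a curve restricted to responders. DOR carries no hypothesis or decision rule. Confidence is high on the wording and low on any particular size. The definition should be corrected before analysis, so that the choice is not made after the deaths are known.

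**What to change.** In Section 11.2:
- Define DOR as the time from first PR or CR to the earlier of PD and death from any cause, in line with PFS.
- Censor responders alive without PD at the last disease assessment showing no progression, and use the same censoring date for PFS. Keep last contact for OS.
- State how deaths long after the last scan are handled, for example by a sensitivity analysis that censors them at the last assessment. Apply the same rule to PFS.

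If PD-only is intended, label the endpoint that way and report the cumulative incidence of PD, with death without PD as a competing event, in place of Kaplan-Meier.

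The cost is a few sentences and one sensitivity analysis. No new data are needed, because Section 5.11 already follows vital status in all participants. The reported DOR will usually be slightly less favourable.
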